#### 4.1.4.1 Administration

The different capsule strengths should not be combined in the same bottle at any time. BI 3011441 capsules must be stored in the containers provided and handled according to the labelled storage instructions and shelf life. Labels will be prepared in accordance with Good Manufacturing Practice (GMP) and local regulatory guidelines.

Patients will be advised to return any unused BI 3011441 in the dispensed bottles, in addition to returning any empty bottles. All patients will be required to complete a patient diary to document BI 3011441 intake, which must be returned to the clinic for review at each clinic visit.

BI 3011441 doses should be taken orally at approximately the same time each morning with the exception of certain trial visit days.

Whenever possible, all doses of BI 3011441 should be taken with water limited to a maximum of 100 mL per capsules and the total amount of water intake should be within the range of 300-500 mL. Capsules should be taken without food, at least 1 hour before a meal or 1 hours after a meal.

For all visits which plan to conduct PK sampling, patients will be asked to fast overnight (minimum of 10 hours) prior to the visit. Pre-dose laboratory samples will be collected prior to receiving the single morning dose.

Missed doses should not be made up if more than 6 hours have passed since scheduled dosing time. Missed doses must be recorded in the patient's diary.

Before initiating a new treatment cycle, all of the following criteria must be met:

- Ophthalmologic exam (if scheduled at the respective cycle visit): No evidence of Retinal Pigment Epithelial Detachment (RPED) or Retinal Vein Occlusion (RVO)
- Echocardiography (if scheduled at the respective cycle visit):
  - No evidence of an absolute decrease in LVEF of 10 percentage points or greater from screening value, to a value that is below institutional lower limit of normal (LLN).
  - No evidence of an absolute decrease in LVEF of 15 percentage points or greater whether below or above institutional LLN, even if the patient is asymptomatic.
- Absence of related clinically significant adverse events: At the planned start of a treatment cycle patients may continue therapy only after recovery to a level which would allow further therapy; i.e. CTCAE Grade 1 or pre-treatment value or considered not clinically significant (except for the following CTCAE Grade 2 AEs: neuropathy, alopecia and fatigue/asthenia).

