#### 4.1.4.2 Dose reductions and dose delays

For the assessment of the severity of adverse events (AEs), CTCAE version 5 ([R18-1357](#)) will be used. Any SAEs/AEs of  $\geq$ Grade 2 deemed intolerable by the patient or the treating physician and not responding to appropriate medical management, and any related SAEs/AEs of  $\geq$ Grade 3 will result in the interruption of treatment with BI 3011441 until resolution to baseline or Grade 1. Please see [section 3.3.4.1](#) for the permanent IMP discontinuation criteria.

Proprietary confidential information © 2020 Boehringer Ingelheim International GmbH or one or more of its affiliated companies

If the treatment interruption is  $\leq 2$  weeks, the patient can be re-exposed to BI 3011441 at the same dose or one dose level lower than the dose administered before the interruption as long as the re-exposure is considered clinically indicated by the Investigator. However, dose reduction is not allowed for patient who uses 4 mg, and the study medication (BI 3011441) needs to be discontinued.

In case the treatment is delayed due to an AE, the patient should visit the site at least once a week for assessment of safety laboratory and AEs. More frequent visits may be appropriate as assessed by the Investigator. Any case of a delay in treatment cycle for more than 2 weeks should be communicated to the Sponsor. The Investigator in agreement with the Sponsor will decide about further treatment of individual patient, based on known risk/benefit of BI 3011441.

A maximum of 1 dose reductions of BI 3011441 are allowed, if lower tested dose levels are available. Dose reductions will be only to doses previously explored in earlier cohorts.

In case of dose reductions, all future dose administrations will also be at the reduced dose level. If that is intolerable (as previously described), the treatment of that patient should be discontinued. Recommendations for dose reductions of BI 3011441 are given in [Tables 4.1.4.2: 1, 4.1.4.2: 2, and 4.1.4.2: 3](#).

Proprietary confidential information © 2020 Boehringer Ingelheim International GmbH or one or more of its affiliated companies

Table 4.1.4.2: 1

Dose modification for BI 3011441 for haematologic and non-haematologic toxicity related to treatment

Haematologic and non-haematologic toxicity	Dose modification
Grade 1	

Continue BI 3011441 at full dose, monitor as clinically indicated.

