Grade 4	

• Immediately refer to the patient for ophthalmologic exam.

• Permanently discontinue BI 3011441.

• Continue monitoring as clinically indicated and provide appropriate medical management as needed.

Table 4.1.4.2: 3 Dose modification for LVEF decrease in BI 3011441

Adverse event	Dose modification
Grade 1	

• Not applicable

Grade 2 a	

• Interrupt BI 3011441 until resolution to the normal institutional range or to within 5 percentage points of the baseline value and then, resume BI 3011441 at the reduced dose by one dose level.

• Continue monitoring as clinically indicated and provide appropriate medical management as needed.

Grade 3 and 4	

• Permanently discontinue BI 3011441.

• Continue monitoring as clinically indicated and provide appropriate medical management as needed.

a An absolute decrease in LVEF of 10 percentage points or greater from baseline value to a value that is below institutional LLN value, OR an absolute decrease in LVEF of 15 percentage points or greater and lower than 20 percentage points whether below or above institutional LLN value

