#### Non-haematologic

- Grade  $\geq 3$  non-haematologic (not laboratory) toxicities despite the use of adequate medical interventions and/or prophylaxis as dictated by local institutional clinical practices, the clinical trial protocol, and/or the judgment of the Investigator. The following exceptions apply:
  - In a patient with pre-existing fatigue at baseline, Grade 3 fatigue will only be considered as a DLT if it lasts for more than 7 days despite adequate medical interventions and baseline fatigue was no more than Grade 1.
  - Grade 3 nausea or Grade 3 vomiting will be defined as a DLT when it persists at Grade 3 longer than 48 hours despite adequate medical intervention
  - Grade  $\geq 3$  diarrhea will be defined as a DLT only when hospitalisation is required, and the event persists at Grade  $\geq 3$  for more than 48 hours despite adequate medical intervention.
  - Hypertension will be defined as a DLT only when a patient was enrolled with controlled hypertension as per the exclusion criteria, and systolic blood pressure has increased  $\geq 160$  mm Hg or diastolic blood pressure increased  $\geq 100$  mm Hg, which cannot be controlled by hypertensive medication and which requires a dose reduction / discontinuation of study drug.
- Any Grade 3 or Grade 4 non-haematologic laboratory value if:
  - Medical intervention is required to treat the patient, except Grade 3 electrolyte abnormality that lasts  $<72$  hours, is not clinically complicated and resolves spontaneously or responds to conventional medical intervention, or
  - The abnormality leads to hospitalisation, or
  - The abnormality persists for  $>1$  week, and considered significant enough to be qualified as DLT in the opinion of the Investigator, and confirmed by the SMC.

Proprietary confidential information © 2020 Boehringer Ingelheim International GmbH or one or more of its affiliated companies

- An absolute decrease in LVEF of 10 percentage points or greater from screening value to a value that is below institutional LLN value, OR an absolute decrease in LVEF of 15 percentage points or greater whether below or above institutional LLN, even if the patient is asymptomatic, will be defined as a DLT if:
  - After holding the trial drug and obtaining a follow-up echocardiography within 4 weeks, LVEF has not returned within the normal institutional range or to within 5 percentage points of the screening value; OR

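### Footnote a to Table 4.1.4.2: 3 caps only one of its two Grade 2 branches at 20 points, so a large LVEF fall to below LLN gets the looser row; the LVEF recovery test also does not fit falls that stay at or above LLN

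*Protocol*

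**What the plan says.** Three parts of the protocol set LVEF rules. The SAP adds none; its Section 5.1 refers back to the protocol for the DLT definition.

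- **Dose modification (Section 4.1.4.2, Table 4.1.4.2: 3).** For Grade 2 the instruction is "Interrupt BI 3011441 until resolution to the normal institutional range or to within 5 percentage points of the baseline value", then to resume one dose level lower. Grades 3 and 4 mean permanent discontinuation. Footnote a defines Grade 2 by two alternatives. The first is "An absolute decrease in LVEF of 10 percentage points or greater from baseline value to a value that is below institutional LLN value". The second is "an absolute decrease in LVEF of 15 percentage points or greater and lower than 20 percentage points whether below or above institutional LLN value". The section introduces its tables as advice: "Recommendations for dose reductions of BI 3011441 are given in" the three tables.
- **New cycle (Section 4.1.4.1).** "Before initiating a new treatment cycle, all of the following criteria must be met". At a visit with a scheduled echo, one criterion is "No evidence of an absolute decrease in LVEF of 15 percentage points or greater whether below or above institutional LLN"; another bars a 10-point fall to below LLN. For related clinically significant events, "patients may continue therapy only after recovery to a level which would allow further therapy; i.e. CTCAE Grade 1 or pre-treatment value", or if judged not clinically significant. Flow Chart footnote f schedules echoes at Cycle 1 Day 15 and Cycle 2 Visit 1.
- **DLT (Section 5.2.6.3).** The trigger is a fall of at least 10 points to below LLN, or of at least 15 points on either side of LLN. It becomes a DLT under sub-criterion 1 if, after a hold and a repeat echo within 4 weeks, "LVEF has not returned within the normal institutional range or to within 5 percentage points of the screening value". Sub-criterion 2 covers a second decline on re-challenge. Separate bullets make DLTs of a related event requiring permanent discontinuation, a related dose reduction in Cycle 1, and a related toxicity of Grade 2 or more that delays Cycle 2 Day 1 by over 2 weeks. A DLT found at the Cycle 2 Day 1 echo counts for the MTD but not for escalation decisions.

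**The concern.** The main point is the footnote. A fall of 20 points or more that ends below LLN meets the first branch and goes to the interrupt-and-resume row. The same fall ending at or above LLN meets neither branch and is left, by elimination, to the Grade 3/4 row. The lower ejection fraction gets the more lenient rule. The choice of row also reaches the DLT count, because permanent discontinuation for a related event is itself a DLT and an interruption with later resumption need not be.

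The second point is narrower. The trigger treats a fall of 15 points or more as toxicity even when LVEF stays above LLN, but the recovery test is passed by any value in the normal range. A value that never left that range passes without improving.

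LVEF decrease is a named risk in Section 1.4.2, and the MTD and the number of patients with DLTs are the primary endpoints.

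**Working it through.** **Inputs.** S = screening LVEF, v = value tested, d = S − v. L = institutional LLN, which the documents do not give; 50% and 55% are assumed.

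- Footnote a, Grade 2: (d ≥ 10 and v < L) or (15 ≤ d < 20)
- DLT trigger: (d ≥ 10 and v < L) or d ≥ 15
- Literal recovery: v ≥ L or d ≤ 5
- New cycle permitted (LVEF part): trigger not met

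**Step 1: the footnote (L = 50).**

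| S to v | d | Position | Footnote a Grade 2? | Row |
|---|---|---|---|---|
| 70 to 48 | 22 | below LLN | yes, first branch | interrupt, then resume lower |
| 75 to 53 | 22 | above LLN | no | Grade 3/4 by elimination |

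Over whole-number pairs with S = 50–80, v ≥ 40 and d ≥ 20:

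- L = 50, below LLN: v = 40 to 49 gives 21 down to 12 pairs, 10 × (21 + 12)/2 = 165. All 165 fit Grade 2.
- L = 50, at or above LLN: 11 + 10 + … + 1 = 66. None fit.
- L = 55: 15 × (21 + 7)/2 = 210 below LLN, all fit; 6 + 5 + … + 1 = 21 at or above, none fit.
- With the cap on both branches: 0 fit.

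These counts check the logic of the wording; they are not patient shares.

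**Step 2: effect on DLT status.** Take a patient above 4 mg with a related fall from 70% to 48% at the Cycle 2 Day 1 echo, and a repeat echo of 56% within 2 weeks (d = 70 − 56 = 14).

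- Treated as Grade 2: 56% is in the normal range, so sub-criterion 1 is not met. The fall is under 15 points, so the LVEF part of 4.1.4.1 permits Cycle 2. If dosing restarts within 2 weeks, the delay bullet is not met. The dose reduction is in Cycle 2, so the Cycle 1 bullet is not met. There is no DLT unless re-challenge or the SMC catch-all produces one.
- Treated under the Grade 3/4 row: permanent discontinuation, hence a DLT.

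Returning to the normal range is not enough by itself. At 52% the fall is still 18 points, 4.1.4.1 still bars Cycle 2, and a hold beyond 2 weeks becomes a DLT anyway.

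**Step 3: the recovery test.** Trigger and literal recovery can hold together only if v ≥ L and d ≥ 15, so S must be at least L + 15: 65% or 70%. On the grid with S = 50–80 and v from 20 to S:

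- Falls of 15 to under 20 at or above LLN: L = 50, (1 + 2 + 3 + 4) + 12 × 5 = 70; L = 55, (1 + 2 + 3 + 4) + 7 × 5 = 45.
- Adding falls of 20 or more: 70 + 66 = 136 and 45 + 21 = 66. Sub-criterion 1 classifies none of these.
- Every other triggered pair is classified: 885 of 885 and 980 of 980.

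Example (L = 50): 70% to 53%, d = 17. The table's resume condition is met; 4.1.4.1 bars a new cycle. If recovery also requires d < 15, no pair meets both trigger and recovery.

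**Step 4: what already catches the Step 3 patient.** At Cycle 2 Day 1, 4.1.4.1 bars dosing while d ≥ 15. Footnote a makes a fall of 15 to under 20 points Grade 2, so once the delay passes 2 weeks it is a DLT. For values at or above LLN, not recovered under the amended test (d ≥ 15) is the same condition as this bar. The amendment therefore changes the call only when an early repeat echo still shows 15 points or more and the fall then improves within 2 weeks. A related fall at the Day 15 echo is covered by the Cycle 1 dose-reduction bullet, and 4 mg patients by discontinuation. Any fall graded 3 or higher is covered by the general non-haematologic bullet or by discontinuation.

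**Step 5: model sensitivity only.** Integrating the Table 7.1:2 prior numerically gives overdose probabilities of 0.129, 0.232, 0.310 and 0.422 at 4, 6, 7 and 8 mg, against 0.128, 0.233, 0.310 and 0.422 in Table 7.1:3. Table 10.2:1 has nine steps in which one DLT is added among six patients at 8 mg. Published overdose probabilities at 8 mg:

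| Scenarios | From | To |
|---|---|---|
| 19–20 | 0.023 | 0.106 |
| 20–21 | 0.106 | 0.274 |
| 21–22 | 0.274 | 0.501 |
| 34–35 | 0.023 | 0.077 |
| 35–36 | 0.077 | 0.207 |
| 39–40 | 0.041 | 0.109 |
| 40–41 | 0.109 | 0.236 |
| 44–45 | 0.025 | 0.082 |
| 45–46 | 0.082 | 0.232 |

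The highest dose under 0.25 changes in one of nine, scenarios 20–21, from 8 mg to 7 mg (re-run: 0.103 to 0.268). In 21–22 it is 7 mg both times.

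**The case against.** - **Grading follows CTCAE v5, not the footnote** (Sections 4.1.4.2 and 5.2.6.1.5), so a 22-point fall to below LLN may already be above Grade 2. This may be so, but the CTCAE text is not in the documents. The footnote is attached to the Grade 2 row and, as written, admits the case. If the two disagree, that is a further reason to align them.
- **A patient still below LLN cannot resume, and sub-criterion 1 catches failure to recover.** Correct. The footnote matters for DLT status only in the patient who recovers quickly, as in Step 2.
- **The restart table and 4.1.4.1 do not truly conflict.** A reader might infer that a site may start Cycle 2 at 53% from 70% because the table allows it. The documents do not support that: 4.1.4.1 is mandatory and the tables are recommendations, so both apply and the stricter governs the cycle start. No precedence sentence is needed.
- **Returning or resolving implies a change.** This is a natural reading and may be the intended one. The text does not say so, and sub-criterion 2 repeats the phrase as the complement, so it does not settle the matter.
- **The SMC reviews DLTs, and Section 4.1.2 has toxicity of Grade 2 or more described patient by patient.** This is a real safeguard in a small trial, and the SMC catch-all is available. It does not make the written definition consistent.

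A reader might also infer that the MTD would be set too high. Step 5 shows only what any extra DLT does to the model. It does not measure how often this wording would lose one.

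**Conclusion.** Both points hold as minor wording defects. The footnote is the more substantive: as written, a fall of 20 points or more is treated more leniently when it ends below LLN than when it ends at or above it. This can change DLT status for a related fall at the Cycle 2 Day 1 echo, above 4 mg, that recovers enough for dosing within 2 weeks. The recovery-test mismatch is real on a literal reading, but existing rules leave few DLT calls open to change.

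The documents give no incidence of such falls, so the number affected among about 12 patients is unknown, and no effect on the MTD is shown. The examples assume an LLN of 50%; the grid results hold in kind at 55%. The footnote's practical weight depends on how CTCAE v5 grades these falls, which could not be checked.

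**What to change.** 1. In footnote a to Table 4.1.4.2: 3, put the under-20-point limit on the first branch as well, and state that all falls of 20 points or more go to the Grade 3/4 row. Check this against CTCAE v5 grading when drafting.
2. In both LVEF sub-criteria of Section 5.2.6.3 and in the Grade 2 row of the table, count LVEF as recovered only if the current test is met and the fall from screening is less than 15 points.

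The cost is a few words in Section 5.2.6.3, the table and its footnote. Both thresholds are already in the protocol, and no new assessments are needed. The downside is possibly a few more holds, discontinuations or DLTs.

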- c) Physical examinations including the measurements of height (screening only) and weight will be done at screening, on Day 1 of each treatment cycle, at the end-of-treatment (EOT) visit, at the 30-day end of residual effect (EOR) visit, and at the follow-up (FU) visits for progressive disease. ECOG performance status will be done at screening, on Days 1 and 15 of Cycle 1, Day 1 of Cycle 2, on Day 1 of every other cycle beginning with Cycle 3, at the EOT visit, at EOR, and at FU visits for progressive disease.
- d) A patient diary will be given to the patient for continuous use through the trial. It should be given to the patient at the start of each cycle. The diary collects information about BI 3011441 taken at home and provides reminders about fasting blood samples. After one week on trial medication, treatment compliance should be discussed with the patient, to ensure that the medication is being taken correctly (no compliance calculation has to be performed). Then at Visit 1 of each cycle and at EOT treatment compliance needs to be checked including compliance calculations.
- e) 12-lead electrocardiograms (ECGs) will be done in triplicate before blood work or other procedures after 5 minutes of rest at screening, see [section 5.2.4](#).
- f) LVEF is measured by echocardiography at screening, Day 15 of Cycle 1, C2V1, then every 2 cycles (i.e. C4V1, C6V1, C8V1, etc.) and EOT. Additional LVEF assessments should also be done if clinically indicated.
- g) Safety laboratory assessments including haematology, serum biochemistry, coagulation, pregnancy tests, urinalysis and virology (only at screening) will be performed locally. If screening laboratory tests are completed within 72 hours prior to first dose, predose samples on Day 1 of Cycle 1 will not be repeated. See [Section 5.2.3](#) for further detail. Pregnancy tests are mandatory for women with child-bearing potential. A serum beta human chorionic gonadotropin ( $\beta$ -HCG) pregnancy test must be done at screening. Thereafter, this test can be done in either serum or urine on Day 1 of each cycle, at the EOT visit, and at EOR.
- h) An ophthalmological assessment must be done at screening, C2V1, C3V1, C4V1 and then every 2 cycles (i.e. C6V1, C8V1, C10V1, etc.) and EOT. Ophthalmological assessment can be done separated  $\pm 2$  day from visit. Additional ophthalmological assessments should also be done if clinically indicated.

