The Safety Monitoring Committee (SMC, see [Section 8.7](#)) will recommend the size for the next dose escalation cohort. After all patients in a cohort have either experienced a DLT or have been observed for at least the MTD evaluation period without experiencing a DLT, the Bayesian model will be updated with the newly accumulated data. The overdose risk will then be calculated for each dose, and escalation will be permitted to all doses which fulfil the EWOC criterion and the additional 50 % escalation rule. Based on the model and on

Proprietary confidential information © 2020 Boehringer Ingelheim International GmbH or one or more of its affiliated companies

additional information (PK, PD, patient profiles), the members of the SMC will reach a joint decision on the next dose level to be investigated.

If DLTs are observed in the first two consecutive patients of a previously untested dose level, subsequent enrolment to that cohort will be stopped. The BLRM will be re-run to confirm that the dose level still fulfils the EWOC principle. Based on this information, the SMC will evaluate whether the next patients will be enrolled at the same dose level, or if they will be enrolled at a lower dose level.

The SMC may recommend stopping the dose escalation phase after the criterion for MTD ([Section 7.1](#)) is fulfilled. Further patients may be included to confirm this MTD estimate, i.e. to confirm that the EWOC criterion is still fulfilled. If no DLT is observed at a dose of which the efficacy is considered sufficient, the SMC may decide to include an additional number of patients at the same dose level and to declare this dose as the recommended.

The SMC can declare any dose fulfilling the EWOC criterion as the RD, independent of the MTD estimate.

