#### 5.2.6.3 Dose limiting toxicities

DLTs will be recorded throughout the trial. Any DLT must be reported to the Sponsor by the Investigator or designee within 24 hours of first knowledge using the same procedure as SAE reporting. Only DLTs occurring in the first 4 weeks (the first cycle) of treatment are considered for dose-escalation decisions made by the SMC. DLTs observed during the MTD

Proprietary confidential information © 2020 Boehringer Ingelheim International GmbH or one or more of its affiliated companies

evaluation period will be considered for MTD determination. In addition, DLT(s) observed during the ophthalmological assessment and echocardiographic assessment of Cycle 2 Day 1 will be considered for MTD determination. However, all AEs and SAEs meeting criteria of DLT observed in all treatment cycles will be considered for determining a RD.

Any of the following AEs will be classified as DLTs if assessed as possibly related to BI 3011441, i.e., unless unequivocally due to underlying malignancy or an extraneous cause and will be reviewed by the SMC.

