  - After holding the trial drug and obtaining a follow-up echocardiography within 4 weeks, LVEF has returned within the normal institutional range or to within 5 percentage points of the screening value, but on re-challenge there is second decline of an absolute decrease in LVEF of 10 percentage points or greater from screening value, whether above or below institutional LLN.
- Symptomatic heart failure
- Any retinopathy  $\geq$  Grade 2
- Retinal vein occlusion of any grade.
- Interstitial lung disease/pneumonitis of any grade
- Hepatic injuries assessed as related to trial drug and which meet the AESI criteria for hepatic injury in [Section 5.2.6.1.4](#)
- Treatment pause of BI 3011441 for  $\geq$ 14 days, or dose reduction in Cycle 1 due to treatment-related AEs
- Any treatment-related  $\geq$  Grade 2 toxicity that persists and results in a more than 2 weeks delay of administration of BI 3011441 on Cycle 2 Day 1
- Any treatment-related AE that would require permanent discontinuation of BI 3011441.

Any other toxicity considered significant enough to be qualified as DLT in the opinion of the Investigators, and confirmed by the SMC, will be reported as a DLT.

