6. GENERAL ANALYSIS DEFINITIONS

6.1 TREATMENT

The trial is an open-label phase I trial with dose escalation, confirmation and expansion of BI 3011441 as monotherapy. For basic study information such as treatments to be administered, assignment of treatment groups, and selection of doses, see CTP Section 4.

For safety analyses, AEs will be classified to one of the following time periods: “Screening”, “On-treatment” or “Follow-up.” This will be applied for all adverse events. Detailed rule for assigning AEs to these time periods are listed below.

- If the date of informed consent \leq AE onset date $<$ date/time of first administration of trial treatment, then the AE is assigned to “Screening”;
- If date of first administration of trial treatment \leq AE onset date \leq date of last administration of trial treatment + 30 days of Residual Effect Period (REP), then the AE is assigned to “On-treatment”;
- If AE onset date $>$ date of last administration of trial treatment + 30 days, then the AE is assigned to “Follow-up”

Table 6.1: 1 Definition of analysis treatment periods for safety analysis

Analysing Treatment Period	Start Date	Stop Date
Screening	Date of informed consent	Date/Time of the first administration of trial treatment
On-treatment	Date of the first administration of trial treatment	Date of the last administration of trial treatment + 30 days of REP
Follow-up	Date of the last administration of trial treatment + 31 days	Date of the last visit
MTD evaluation period*	Date of the first administration of trial treatment	Date of the first administration of trial treatment + 28 days (i.e., treatment cycle)

*The MTD evaluation period is only applied to the patients in the dose escalation part of the trial.

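### A DLT that can be completed only after Day 28 is shut out of the escalation model, and the plan has no rule for a patient whose case is still pending

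*Protocol*

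**What the plan says.** Protocol 5.2.6.3 lists the DLT criteria. Two matter here.

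- **Delay criterion.** A related toxicity of Grade 2 or higher that persists and "results in a more than 2 weeks delay of administration of BI 3011441 on Cycle 2 Day 1".
- **LVEF criterion.** A fall in LVEF becomes a DLT only after a second step. Either "After holding the trial drug and obtaining a follow-up echocardiography within 4 weeks, LVEF has not returned" to the stated range, or it has returned "but on re-challenge there is second decline of an absolute decrease in LVEF of 10 percentage points or greater from screening value".

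On timing, the same section states: "Only DLTs occurring in the first 4 weeks (the first cycle) of treatment are considered for dose-escalation decisions made by the SMC". It adds one exception: DLTs seen at the eye and echocardiographic assessments of Cycle 2 Day 1 count for MTD determination. DLTs from all cycles count for the recommended dose (RD).

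Section 2.1.1 sets the MTD evaluation period at 28 days and plans a BLRM rerun with all DLTs when escalation ends. Section 3.1 says that once each patient has had a DLT or has been "observed for at least the MTD evaluation period without experiencing a DLT, the Bayesian model will be updated". SAP Table 6.1:1 ends the MTD evaluation period at "Date of the first administration of trial treatment + 28 days (i.e., treatment cycle"). The text of SAP 6.1 assigns adverse events to the screening, on-treatment and follow-up periods by onset date.

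**The concern.** The delay criterion describes a toxicity that would usually begin in Cycle 1 but qualifies as a DLT only in Cycle 2. By then the model may already have been updated and the next dose opened. A cohort could be scored 0/3 while one of its patients is off drug for a related toxicity that later meets the protocol's own DLT definition. That would bias the DLT rate downward in the calculation that controls overdose risk, and the next cohort would bear the consequence. Cohorts are of three, and Section 3.1 lets escalation rest on two evaluable patients without a DLT, so a single patient carries much weight. The log for Amendment 1 says the DLT conditions were changed so that DLTs would not be underestimated, and this gap works against that aim.

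**Working it through.** **Timing.** Inputs: 28-day cycles, so Cycle 2 Day 1 is Day 29 (window ±2 days). On the echo schedule, the Flow Chart says "LVEF is measured by echocardiography at screening, Day 15 of Cycle 1, C2V1".

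- Delay criterion: more than 14 days after Day 29 gives 29 + 15 = Day 44 at the earliest (Days 42 to 46 with the visit window).
- LVEF fall first seen at Cycle 2 Day 1: a repeat echo after a hold comes after Day 29, and at the latest on 29 + 28 = Day 57.
- LVEF fall seen on Day 15: the repeat echo is due by 15 + 28 = Day 43. That is an upper limit, so confirmation before Day 28 is possible.
- Second LVEF fall on re-challenge: in practice after Day 28, because the next scheduled echo is at Cycle 2 Day 1. An unscheduled echo could show it sooner.

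**How a patient on hold is classified at Day 28.** Inputs: a pause of 14 days or more is itself a DLT (5.2.6.3). More than 8 missed doses for reasons other than a DLT makes the patient replaceable (3.3.4.1.2). Doses missed by Day 28 = 28 − start day + 1.

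| Hold starts | Doses missed by Day 28 | Status at Day 28 |
|---|---|---|
| Day 15 | 14 | DLT through the pause criterion |
| Days 16-20 | 13 down to 9 | No 14-day pause yet; may be replaced, and replaced patients are excluded from the MTD (7.3.2) |
| Day 21 or later | 8 or fewer | No 14-day pause, not replaceable on this ground; can enter the model as no DLT |

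**Effect of one such patient.** The model is logit(π_d) = log α + β·log(d/8), with the three-component prior of Table 7.1:2 and a binomial likelihood, integrated numerically on a grid. The prior interval probabilities agree with Table 7.1:3 within 0.006. The rows of Table 10.2:1 that were rerun (1-9, 13, 16-18, 20, 21) agree within 0.02. P(OD) is the posterior probability that the DLT rate is at least 0.33; EWOC requires it to be below 0.25.

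| Data | Protocol recommendation | Protocol P(OD) at that dose | Recomputed |
|---|---|---|---|
| Scenario 1: 4 mg 0/3 | 6 mg | 0.095 | 0.094 |
| Scenario 2: 4 mg 1/3 | 4 mg | 0.194 | 0.205 |
| Scenario 6: 4 mg 0/3, 6 mg 0/3 | 8 mg | 0.185 | 0.196 |
| Scenario 7: 4 mg 0/3, 6 mg 1/3 | 6 mg | 0.153 | 0.148 |

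The table does not print P(OD) for the higher doses once the late DLT is counted. Recomputed:

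- 1/3 at 4 mg: P(OD) at 6 mg is 0.403, against 0.094 with 0/3.
- 0/3 at 4 mg and 1/3 at 6 mg: P(OD) is 0.276 at 7 mg and 0.430 at 8 mg, against 0.074 and 0.196 with 0/3 at 6 mg.

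All three fail EWOC once the DLT is counted. The 7 mg value is the closest, 0.276 − 0.25 = 0.026 above the limit. The protocol's own row supports it: the recomputed target-interval probability is higher at 7 mg (0.460) than at 6 mg (0.418), so a recommendation of 6 mg fits with 7 mg having failed EWOC.

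**The case against.** The other side has real substance.

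- **The SMC decides, not the model alone.** Under Section 4.1.2 all Grade 2 or higher toxicity in the evaluation period is described for each patient in the cohort, so the toxicity would be in view. Section 5.2.6.3 lets the SMC confirm other toxicities as DLTs. Section 3.1 requires observation for at least the period, so waiting is allowed. Details sit in an SMC charter that is not among the documents. This stands as mitigation, but it is discretionary. Nothing stated requires a wait or puts the pending case into the EWOC calculation.
- **Dating by onset.** If the onset rule in SAP 6.1 extends to the MTD evaluation period, a Cycle 1 toxicity that later delays Cycle 2 falls inside it. That reading is reasonable, but the rule is written out only for the other three periods. It also would not help at Day 28, when the criterion has not yet been met.
- **The effect is generic.** Any DLT in a cohort of three can change the recommendation, and the documents give no frequency for pending cases. This is correct: the calculation shows consequence, not likelihood.

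A reader might infer that both criteria can be met only after Day 28. The LVEF criterion can be met within Cycle 1 after a Day 15 fall, so this is too strong. A reader might also infer that the delay DLT never reaches a final model. Section 2.1.1 reruns the BLRM with all DLTs at the end of escalation, and the onset reading could bring the event into the main MTD analysis, so the documents do not support that either.

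**Conclusion.** The concern holds in a limited form. One listed DLT criterion cannot be completed before about Day 44, and LVEF falls first seen at Cycle 2 Day 1 (in practice also second falls on re-challenge) are confirmed after Day 28. The escalation rule nevertheless admits only first-4-week DLTs. The Cycle 2 Day 1 exception does not close the gap: it is worded for MTD determination, it omits the delay criterion, and an LVEF fall seen on that day is not yet a DLT.

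The exposed route is a hold starting at about Day 21 or later, where the patient can be scored as no DLT. For holds starting on about Days 16-20 the patient may instead be replaced and drop out of the MTD data. One such patient is enough to reverse the model's recommendation after the 4 mg or the 6 mg cohort. Late DLTs still count for the RD, but that comes after the escalation decision.

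This assumes cohorts of three evaluable patients, as in Appendix 10.2, and that a DLT occurs on the day its criterion is met, which no passage confirms or denies. It is more than missing detail, because a stated rule keeps a DLT that the protocol itself defines out of the decision it should inform.

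**What to change.** Reconcile Protocol 2.1.1, 3.1 and 5.2.6.3 with SAP 6.1 and Table 6.1:1.

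1. State that, for the MTD evaluation period, a DLT is dated by onset of the underlying toxicity, and that toxicities found at the Cycle 2 Day 1 assessments are included. State that this applies to escalation decisions as well as to MTD determination.
2. State how a patient with an unresolved Cycle 2 Day 1 delay or LVEF hold is handled at a model update. Either the patient is not yet complete and the update waits, or the escalation BLRM is also run with that patient counted as a DLT and the SMC receives both results.
3. Align the end of the period. First dose + 28 days in the SAP is study Day 29, whereas a 28-day cycle ends on Day 28.

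The cost is wording and, only when a case is pending, one extra model run or a wait of about 2-4 weeks (44 − 28 = 16 days for the delay; 57 − 28 = 29 days for the latest repeat echo). The re-challenge limb has no stated end date, so the second run is the practical choice there. No DLT criterion or dosing rule changes.
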